In a recent Cochrane review of LMAs vs ETTs in obese patients, the authors concluded that there was a significant improvement in oxygenation during and after surgery, including better pulmonary performance of the second-generation LMA. They also reported less postoperative coughing, suggesting a better recovery for patients [26]. Another prospective study evaluating the use of LMA vs. ETT in moderately obese patients undergoing peripheral surgeries concluded that the LMA group had better early postoperative lung function and pulse oximetry saturation compared with the ETT group [27].

Compared to airway management with an ETT, the use of LMAs resulted in a shorter PACU stay and a faster discharge home [14]. In a hospital such as Parkland with a busy surgical service and limited resources, the associated cost savings could be significant [28].

There has been inconclusive evidence of whether obese patients have higher gastric volumes compared to lean patients but recent articles report that there does not seem to be a link between obesity and delayed gastric emptying [29-32]. Gastric ultrasound is a noninvasive tool to examine stomach contents at the bedside and is feasible in lean and severely obese patients [33, 34]. The antrum is highly amenable to ultrasound imaging and accurately reflects the content of the entire stomach [35]. A volume of < 1.5mL/kg suggests low gastric volumes and a low risk of aspiration [36].

Concise Summary of Project:

This prospective, randomized, comparative study is intended to enroll a total of 150 obese patients with a BMI >30 kg/m² undergoing surgery at Parkland Hospital. There will also be a second site (MD Anderson) that will enroll an additional 150 obese patients. The efficacy and performance of the second-generation LMA will be compared to endotracheal intubation. A standardized anesthetic protocol that is usual and customary for the type of operation the patient is having will be provided to the anesthesia teams of enrolled subjects. The remainder of the anesthetic care of the subject will not deviate from the standard of care.

Study Procedures:

Screening and Informed Consent

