A member of the research team will use a screening form to look for surgical patients that meet all the inclusion and exclusion criteria. He/she will approach potential subjects in the preoperative area and the study will be explained in detail in a private room. Patients will be informed that they will receive no compensation for participating in the study and there will be no adverse consequences if they choose not to participate. If the subjects agree to participate, informed written consent will be obtained prior to any study procedures and this document will be sent to [contact], for inclusion in the patient's medical record, per Parkland regulations. The study duration will be from the beginning of anesthesia care to 2 hours after the patient's surgery ends.

Anesthetic Protocol

The anesthesia team that will be caring for the subject during surgery will be given the protocol for the study, which standardizes the general anesthetic technique.

Subject Group Assignment:

A randomization schedule will be created by a member of the research team that is not involved in clinical care (i.e., statistician). Subjects will be randomized to receive either a standard endotracheal tube or a second-generation LMA. The ETT size will be selected based on gender- 7.0 for women and 8.0 for men. LMA sizing will be according to manufacturer guidelines.

In the preoperative holding area, a gastric ultrasound will be performed to rule out the presence of significant gastric contents. This will be done with a curved array low-frequency transducer on the current ultrasound machine that is already available in the preop area. No visible contents in the gastric antrum in either the supine or right lateral decubitus (Grade 0) provides unequivocal diagnosis of an empty stomach. A threshold of 1.5 mL/kg will be the upper limit of acceptable gastric volume. Any patients who has more than this volume will not undergo any further study procedures.

Once the patient is in the operating room, they will be positioned on the operating room table and standard ASA monitors will be applied. All patients will undergo a standard anesthetic induction. Patients who are randomized to endotracheal intubation will also have a neuromuscular blocking agent (i.e., rocuronium) administered to facilitate intubation.

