A blinded research assistant will perform all postoperative assessments. All patients will go to the post anesthesia care unit (PACU) after surgery, unless an intraoperative complication necessitates that the patient go to the intensive care unit (ICU), at which time they would no longer be a part of the study. As patient-reported outcomes have become increasingly important for hospitals, treatments that have the potential to increase patient satisfaction are being studied closely. The postoperative quality recovery scale (PQRS) is a tool that assesses recovery over time and compares them to baseline values. Some of the advantages of the PQRS are that it is validated, takes less than 5 minutes to administer, has a low patient refusal rate, and is acceptable to patients across a wide range of ages. The PQRS will be administered at baseline in the preoperative area, and after PACU arrival at 15 minutes and again at 45 minutes and 80 minutes (Appendix 1). The time when the patient arrives to the PACU, is ready for discharge from the PACU (modified Aldrete score \geq 9) and actual discharge from the PACU will be recorded.

After the first ten patients have been enrolled, the PI and the research team will review the cases to make any adjustments to the protocol to better facilitate data collection for the remaining study participants.

Data Sources

Protected health information including name, medical record number, and date of birth will be recorded and stored securely in a password-protected, secured Excel database. De-identified data will be entered in RedCap data management system.

Parameters:

- 1. Protected health information (PHI): name, medical record number, date of birth, phone number
- 2. Demographic information (age, weight, height, BMI, gender), medical and surgical history, ASA)
- 3. Intraoperative parameters
 - Baseline vital signs upon arrival to operating room
 - Time of induction
 - Intraoperative vitals (systolic, diastolic, and mean blood pressures, heart rate)
 - ECG rhythm
 - Laryngoscopy details (Cormack Lehane view, blade used)
- 4. Adverse event monitoring
 - LMA unable to be inserted after 3 attempts
 - Patient unable to be intubated (e.g., difficult airway)
 - Prolonged hypoxia (> 1 min at <92%) from anesthesia start to anesthesia stop
 - Respiratory adverse event including bronchospasm, laryngospasm aspiration, reintubation
 - Prolonged PACU stay (> 2 hours)
 - Unplanned hospital admission

Criteria for Inclusion of Subjects:

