- 18-80 years old
- Obese BMI \geq 30 kg/m²
- Scheduled for a non-emergent surgery that requires general anesthesia (e.g., orthopedic, breast, urological, colorectal, ENT, vascular, general surgery)
- Willing and able to consent in English or Spanish
- No current history of advanced pulmonary or cardiac disease

Criteria for Exclusion of Subjects:

- Age less than 18 or older than 80
- BMI >50 or < 30 kg/m²
- Patient does not speak English or Spanish
- Expected surgical duration longer than 4 hours
- Planned postoperative ICU admission
- Patient refusal
- Monitored anesthesia care (MAC) or regional anesthesia without general anesthesia
- Pregnant or nursing women
- "Stat" (emergent) cases
- Known or suspected difficult airway
- Appearance of residual gastric volume >1.5 mL/kg on preoperative gastric ultrasound
- Full stomach/significant aspiration risk (gastroparesis, emergency surgery, untreated moderate to severe gastroesophageal reflux disease, hiatal hernia)
- No history of gastric surgery
- Surgery in position other than supine (e.g., Trendelenburg)
- Laparoscopic surgery

Sources of Research Material:

- Identifying patient information including name, medical record number, and birth date
- Medical history
- Surgical history
- Weight and height
- Laboratory studies
- Vital signs
- Intraoperative anesthetic record

Recruitment Methods and Consenting Process:

A member of the research team will approach subjects who meet all inclusion and exclusion criteria on the day of surgery in a private room. All study procedures will be explained to the patient in layman's terms. If the subject agrees to participate, he or she will sign the consent form and HIPAA Authorization Form prior to any study procedures.

Potential Risks:

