There is some risk to subjects by participating in this study. The anesthetic management of subjects will not differ from the standard care. Patients will be randomized to be intubated with an endotracheal tube or have an LMA inserted as part of the airway management for their surgery. There is a very small risk of aspiration anytime a patient undergoes general anesthesia. A LMA is not considered a 'secured airway' because there is no cuff in the patient's trachea. Therefore, there is a risk of aspiration with a LMA. However, the overall incidence of aspiration with general anesthesia is very low (approximately 1 in 5000 general anesthetics) and no studies have been powered to look directly at aspiration. From existing studies, the LMA groups did not have a higher incidence of aspiration compared with the ETT groups [5, 39, 40]. One caveat is that patients at risk for aspiration have been excluded from these studies, which will also be done for this study. Currently there is no evidence to suggest that the use of a LMA (especially a second generation LMA) in appropriately selected patients increases the risk of aspiration compared with ETT [27].

Study Procedure/Intervention

The table below will be included in the consent form and lists the risks of ETT vs LMA placement.

Risks of Endotracheal Tube (ETT)

Frequent	Occasional	Rare
30% of subjects	15% of subjects	Less than 1% of
30% of subjects	15% of subjects	

Serious		Incorrect placement Difficult intubation	Tracheal perforation Aspiration Tracheal stenosis
Less Serious	Sympathetic surge (increased heart rate and blood pressure)	Trauma to vocal cords, trachea, soft tissues Bronchospasm (lower airway obstruction) Laryngospasm (upper airway obstruction) Dental damage	
Minor	Sore throat Cough	Minor bleeding Laryngeal edema (swelling of the throat) Lip damage Dysphonia (hoarseness) Dysphagia (difficulty swallowing)	

Risks of Laryngeal Mask Airway

	Frequent 30% of subjects	Occasional 15% of subjects	Rare Less than 1% of subjects
Serious		Difficult placement	Aspiration
Less Serious	Sympathetic surge (increased heart rate and blood pressure)	Bronchospasm (lower airway obstruction) Laryngospasm (upper airway obstruction) Local tissue injury	Dental damage
Minor	Sore throat Cough	Minor bleeding Laryngeal edema (swelling of the throat) Lip damage Dysphonia (hoarseness) Dysphagia (difficulty swallowing)	

Psychological Stress

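### The gastric surgery line in the exclusion list is worded in reverse: as written it excludes patients who have not had gastric surgery

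*Combined protocol and SAP*

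**What the plan says.** The section "Criteria for Exclusion of Subjects" has 15 bullets. The thirteenth reads "No history of gastric surgery". It follows the bullets on gastric volume at ultrasound and on aspiration risk, and comes before those on patient position and laparoscopy.

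The inclusion list just above has five bullets. One has the same grammatical form: "No current history of advanced pulmonary or cardiac disease".

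Four other places bear on how the line is read:

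- Recruitment Methods and Consenting Process says staff will "approach subjects who meet all inclusion and exclusion criteria on the day of surgery". Screening and Informed Consent describes the use of a screening form in similar terms.
- The Concise Summary of Project says the study is "intended to enroll a total of 150 obese patients" at the first site, with a further 150 at a second. The inclusion criteria name a broad range of surgical specialties.
- Subject Group Assignment sets a gastric ultrasound limit of 1.5 mL/kg and adds: "Any patients who has more than this volume will not undergo any further study procedures".
- Potential Risks, discussing earlier trials, says that "patients at risk for aspiration have been excluded from these studies, which will also be done for this study".

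**The concern.** A line in an exclusion list makes a patient ineligible when it is true of that patient. Under that convention the gastric surgery line bars patients who have never had gastric surgery and leaves those who have had it to be judged on the remaining criteria. Followed literally, it would turn a trial in general obese surgical patients into one restricted to people with previous gastric surgery.

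The more likely course is that staff mentally reverse the line and enrol accordingly. Then every enrolled patient without that history is in technical breach of a written exclusion criterion, and the population actually studied is defined by an unrecorded correction rather than by the protocol. With two sites, nothing in the document ensures that both make the same correction.

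**Working it through.** No figure in the plan depends on this line, so the check is a count and a comparison of texts.

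**Step 1: count and direction.** The 15 exclusion bullets concern, in order: (1) age, (2) BMI, (3) language, (4) length of operation, (5) planned intensive care, (6) refusal, (7) no general anaesthetic, (8) pregnancy or nursing, (9) emergency cases, (10) difficult airway, (11) gastric volume on ultrasound, (12) aspiration risk, (13) gastric surgery, (14) position, (15) laparoscopy. Bullets 1 to 12, 14 and 15 each state something that disqualifies: 12 + 2 = 14. Bullet 3 is phrased negatively but points the right way, since it mirrors the inclusion requirement to consent in one of two languages. Bullet 13 is the only one worded as a condition that an eligible patient would satisfy: 15 − 14 = 1.

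**Step 2: could the recruitment wording rescue it?** That wording speaks of patients who meet both sets of criteria, so both readings were tried.

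| Reading of an exclusion bullet | Bullet 13 | Other 14 bullets |
|---|---|---|
| True of the patient means not eligible | Reversed | Consistent |
| A condition the patient must satisfy | Consistent | Reversed (a patient would, for example, have to refuse) |

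Neither reading makes all 15 consistent. The first leaves one anomaly and the second leaves 14, so the first is the working convention and bullet 13 is the anomaly.

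**Step 3: comparison with the inclusion list.** "No current history of advanced pulmonary or cardiac disease" works where it stands because it is a condition to be met. "No history of gastric surgery" has the same form under the opposite heading. That suggests an inclusion-style line placed in the wrong list, or a stray negation.

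**Step 4: fit with the rest of the document.** The Concise Summary and the inclusion criteria describe obese patients having many kinds of surgery, with no restriction to those who have had gastric surgery. No other section treats gastric surgery as an eligibility matter, so nothing supports or corrects the literal rule.

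**Step 5: the aspiration statement.** The literal rule also appears at odds with the Potential Risks commitment to exclude patients at risk of aspiration. This is weaker evidence. The document nowhere names gastric surgery as an aspiration risk, and bullet 12, which lists such risks, does not include it. The link rests only on where the line is placed, and the finding does not need it.

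**The case against.** The strongest reply is that this is an obvious slip. The literal rule is so far from the study described that no reader is likely to adopt it. The screening form, which is not in the document, may already be worded correctly. The monitoring board is to review all enrolments and can take up protocol violations, so a route for settling an eligibility query exists. The intended meaning is also inferred rather than stated, and the Potential Risks text does not mention gastric surgery.

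Much of this stands. The practical exposure is small, the intent is an inference, and the aspiration argument is only supporting. This is better described as a drafting inconsistency than as a design decision. It does not remove the defect. The line is an operative eligibility rule, not background text, and it is wrong under its heading. A correctly worded form would limit the consequences but would then disagree with the protocol it implements. Board review can detect an eligibility query but does not supply the missing rule.

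**Conclusion.** The concern holds. One of 15 exclusion bullets is reversed, and no other text in the protocol and SAP puts it right. It should be corrected, but it does not threaten the trial's validity: no bias between arms is claimed, and power, type I error and sample size are unaffected. The ultrasound limit and the other 14 exclusions apply whichever way the line is read.

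The conclusion rests on the ordinary convention that a true exclusion statement removes the patient, which the other 14 bullets follow. It does not rest on any clinical view of gastric surgery. The number of enrolled patients affected is unknown, because the document gives no rate of prior gastric surgery and the screening form is not available.

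**What to change.** - **Amend the line.** The sponsor should reconcile it with its heading, and with the aspiration statement in Potential Risks, in a one-line amendment that says plainly which patients are excluded. By way of example, moving the line unchanged to the inclusion list and deleting its negation in the exclusion list would give the same rule. The choice of rule is the sponsor's.
- **Check the screening form at each site** for the same wording, and align it with the amended text.
- **Check enrolled patients against the reconciled rule.** Data Sources, under Parameters, already lists "medical and surgical history", so no new data are needed. Planned enrolment is 150 + 150 = 300, so this is at most a review of 300 records. It should be done before the coding key or identifiers are destroyed at the end of the project, as Procedures to Maintain Confidentiality provides, because tracing patients back to source records may not be possible afterwards.

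The cost is one line of text, a form check and a record review. Study procedures, sample size and analysis stay as they are.

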Appendix 1: Postoperative Quality Recovery Scale evaluation at baseline, T15, T45, T80

Demographic and Preoperative Data ^a		
Age	yrs	
Gender	Male or Female	
ASA Status	1 2 3 4	
Weight	kg	
Height	in	
BMI	kg/m ²	
Education	Highest level finished:	
Alcohol consumption	units/wk	
Smoking status	Never, used to but quit, current smoker	
Employment	Unemployed	
	Employed and plan to return	
	Employed but plan not to return	
	Occupation:	
	Approximate hrs/wk:	
Inpatient	Yes or No	
Surgical procedure		
Physiological Factors ^{a,d}		
P1 Blood Pressure		
Please record the patient's blood		
pressure	3= SBP 90-140; 2= SBP 70-89 or 141-180;	
	1= SBP <70 or >180	
P2 Heart Rate		
Please record the patient's heart rate		
	3= 45-100; 2= 35-44 or 101-139; 1= <35 or >140	
P3 Temperature	Method 1. Sublingual 2. Tympanic 3. Esophageal	
Please record the patient's	3= 36-37.6; 2= 35-35.9 or 37.7-38.9; 1= <35 or >39	
temperature		
P4 Respiration		
Please record the patient's respiratory	/breaths per minute	
rate	2. Our set of the initial data and the set of the set	
P5 Oxygen use to maintain SpO ₂	3= Oxygen administered by protocol or not	
Please record oxygen requirement	required	
	2= Any SpO ₂ <95% requiring oxygen as an	
	intervention 1= Any SpO ₂ <90% requiring oxygen as an	
	intervention	
P6 Airway	3= Self-maintenance of airway	
Please record the number	2= Maintenance of airway with support	
corresponding to the assessment	(describe)	
conceptioning to the assessment	1= Device in situ	
P7 Agitation	3= Shows no signs of agitation	
Please record the number	2= Patient shows occasional agitation	
corresponding to the assessment	1= Patient shows severe agitation	
P8 Alertness	5=Awake, following commands	
Please record the number	4=Responds to name spoken in normal tone	
corresponding to the actual	3=Responds only after name is spoken loudly	
assessment	and repeatedly or both	
	2=Responds only after mild prodding/	
	shaking	
	1=Does not respond to mild prodding/shaking	
TU112015-050, [name], FormA-ResearchProtocol, Mod 15, 07-28-21 (4)		

P9 What is the level of your strength now? Please record the number corresponding to the actual	3= No weakness 2= A little weak 1= Very weak			
assessment				
Nociceptive Factors ^{a,b,c,e,f}				
N1 I am going to show you a series of faces and I would like you to indicate which face, number or description most accurately describes your level of pain at the moment.	Image: No pain Mild pain Moderate pain Severe pain Worst pain possible			
N2 I am going to show you a series of faces and I would like you to indicate which face, number, or description most accurately describes your level of feeling nauseous or vomiting at the moment.	I 2 3 4 5 No nausea or vomiting Mid nausea Moderate nausea Severe nausea Dry retring or vomiting			
N3 Sore throat Please record the number corresponding to the actual assessment	 0= No sore throat 1= Mild sore throat (complains of sore throat only on asking) 2= Moderate sore throat (complains of sore throat on his/her own) 3= Severe sore throat (change of voice or hoarseness, associated with throat pain) 			
N4 Hoarseness Please record the number corresponding to the actual assessment	0= No hoarseness 1= Hoarseness at the time of interview, but noted only the patient 2= Hoarseness that is readily apparent, but mild 3=Hoarseness that is readily apparent and severe or aphonia			
Emotional Factors ^{a,b}				
E1 I am going to show you a series of faces and I would like you to indicate which face, number, or description accurately describes to what extent you feel sad, low, or depressed at the moment.	Image: Constraint of the sector of the se			
E2 I am going to show you a series of faces and I would like you to indicate which face, number, or description accurately describes to what extent you feel anxious or nervous at the moment.	Image: Constraint of the revolus Image: Constraint of the revolus Image: Constraint of the revolus Image: Constraint of the revolus Image: Constraint of the revolus Image: Constraint of the revolus Image: Constraint of the revolus Image: Constraint of the revolus Image: Constraint of the revolus Image: Constraint of the revolus Image: Constraint of the revolus Image: Constraint of the revolus Image: Constraint of the revolus Image: Constraint of the revolus Image: Constraint of the revolus Image: Constraint of the revolus Image: Constraint of the revolus Image: Constraint of the revolus Image: Constraint of the revolus Image: Constraint of the revolus Image: Constraint of the revolus Image: Constraint of the revolus Image: Constraint of the revolus Image: Constraint of the revolus Image: Constraint of the revolus Image: Constraint of the revolus Image: Constraint of the revolus Image: Constraint of the revolus Image: Constraint of the revolus Image: Constraint of the revolus Image: Constraint of the revolus Image: Constraint of the revolus Image: Constraint of the revolus Image: Constraint of the revolus Image: Constrate of the revolus Image: Constraint of			
E3 What is the overall level of satisfaction with your immediate postoperative recovery (from the time surgery ended until now)- *T80 assessment only a. Patient questionnaire adapted from Royse et al. 2010 and Amor	1-100 scale 100 = "completely satisifed" 90 = "mostly satisfied" 80 = "moderately satisfied" 70 = "minimally satisfied" < 70 = "not satisfied" and write reason here			

Patient questionnaire adapted from Royse et al. 2010 and Amorim et al. 2014 Pain, depression, and anxiety scales are modified from Wong and Baker 1988 Nausea scale is modified from Baxter et al. 2011 Alertness scale adapted from Doufas et al. 2001 Sore throat scale adapted from Chattopadhyay 2017 Hoarseness scale adapted from Park 2010

b.

c.

d.

e. f.
